### 5.2. Safety Analysis Set

This set consists of randomized subjects receive at least one dose of study medication. Subjects will be analyzed according to treatment received, ie, as treated.

### 5.3. Other Analysis Sets

#### 5.3.1. Per-Protocol Analysis Set

The Per-Protocol (PP) analysis set will consist of the subjects in the MITT population, who in addition:

- Have completed a minimum of 10 days of treatment with IV anidulafungin, unless declared a clinical and/or microbiologic failure;
- Have received total antifungal treatment (IV only, IV+Oral) for a minimum duration of 14 days, unless declared a clinical and/or microbiologic failure;
- Have not received more than 48 hours of systemic antifungal therapy (for treatment of current *Candida* infection) prior to first dose of study drug;
- Must not have a prosthetic device and/or vascular catheter (including central venous catheter or an implantable port) at a suspected site of infection are to be excluded, unless the device is removed at study entry or soon after first dose of study drug;

- Have not taken more than 1 day of protocol prohibited antifungal therapy concomitant with study therapy, unless declared a clinical and or microbiologic failure;
- Have reached the 6 weeks Follow up visit unless the subject died or withdrew consent prior to 6 week follow up;

And also exclude those subjects with protocol violations that could have an impact on the efficacy endpoints (See [Section 5.3.2](#)).

### **5.3.2. Pk Analysis Set**

The first 6 subjects aged between 1 month to <2 years will constitute the PK sub-study population. Their data will be combined with all other subjects' safety data for the analyses using the safety population. In addition, demography, medical history, adverse events and efficacy (in those subjects who received anidulafungin as monotherapy for treatment purposes) will be summarized for these 6 subjects alone, and patient profiles will be generated for each of these subjects to allow examination of all their data. They will be presented as a separate group within the listings.

### **5.3.3. Safety ANALYSIS SET**

This set consists of all subjects who have received at least one dose of study medication.

### **5.4. Treatment Misallocations**

Not Applicable.

### **5.5. Protocol Deviations**

The following sections describe any protocol deviations that relate to the statistical analyses.

It is possible that unexpected deviations will arise, becoming known only after the study has been active for a long period of time; hence more deviations may be added. A full list of protocol deviations for the study report will be compiled prior to database closure. As of this writing, the protocol deviations can all be found in [Section 5.5.1](#) and [Section 5.5.2](#) below.

Only protocol deviations that are thought to affect the primary efficacy endpoint will be considered.

#### **5.5.1. Deviations Assessed Prior To Treatment Administration**

At screening, the investigator will assess subjects against the inclusion and exclusion criteria as set out in Sections 4.1 and 4.2 of the protocol. Granted exceptions to the inclusion or exclusion criteria are not expected to occur. Any subject who enters the study when the inclusion or exclusion criteria would have prevented entry will be considered to have had a protocol deviation.

### 5.5.2. Deviations Assessed Post-Treatment Administration

Any significant deviation from the protocol will be reviewed prior to database closure and a decision taken regarding evaluation for each analysis population.

- If switched to fluconazole, and not all switching criteria, as listed in Section 5.1 of the protocol were met;
- Receipt of any excluded concomitant medications;
- Receipt of the incorrect dose, not including allowed dose escalations and reductions;
- Incorrect administration of treatment;
- Incorrect duration of treatment;
- Non-compliance to study medication, which means a subject should have taken at least 80% of his/her planned doses.

## 6. ENDPOINTS AND COVARIATES

This section defines endpoints and covariates only. Statistical analysis details are found in [Section 8](#).

### 6.1. Efficacy Endpoint(s)

The efficacy endpoints are all secondary endpoints.

#### 6.1.1. Global Response at the End of IV Treatment (EOIVT)

##### 6.1.1.1. Global Response Determination at EOIVT

Global response at EOIVT is based on assessment of clinical and microbiological response provided by the investigator at this time point, and will be programmatically determined as follows:

**Success:** A patient will be categorized as having successful response if there is a clinical response of cure or improvement and microbiological eradication or presumed eradication.

**Failure:** A patient will be categorized as having an unsuccessful response if there is a clinical response of failure and/or unsuccessful microbiological response (persistence or new infection at FU or relapse at FU).

**Indeterminate:** A patient will be categorized as indeterminate if there is a clinical response of indeterminate and /or microbiological response of indeterminate and neither clinical response is a failure nor unsuccessful microbiological response (persistence or new infection or relapse).

A global response determination of failure at EOIVT will be carried forward programmatically to all subsequent visits.

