#### **6.10. Discontinuation Criteria for Persistent Candidemia**

Subjects who were either candidemic at baseline or become candidemic during the course of the study will be considered treatment failures and discontinued from study treatment if candidemia persists for more than 7 days.

Note: These subjects will be discontinued from study treatment but will remain in the study for safety monitoring according to the procedures described in [Section 6.7](#). These subjects are required to return for the 2- and 6-week follow-up visits.

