## 7.3. Global Response Determination

Efficacy will be based on a determination of global response (combination of clinical and microbiological response) of success or failure at the EOIVT, EOT and FU visits. Rates of relapse (recurrence) and/or new infection will be assessed at the FU visits. These efficacy parameters will be derived in the analysis from the investigator's assessment of clinical and microbiological response, and are defined below.

Global response, which will be derived from both investigator assessed clinical and microbiologic responses, will be defined as follows:

- **Success:** A subject will be categorized as a success if there is both a clinical success (cure or improvement) and microbiological success (eradication or presumed eradication);

- **Failure**: A subject will be categorized as a failure if there is either a clinical or microbiological failure (excluding clinical and microbiological responses of indeterminate);
- **Indeterminate**: A subject will be categorized as indeterminate if there is a clinical and/or microbiological response of indeterminate and neither response was a failure.

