#### **7.4. Clinical and Microbiologic Response Assessment**

##### **7.4.1. Subjects with Invasive Candidiasis/Candidemia (Except for Subjects with *Candida* Endocarditis or *Candida* Osteomyelitis)**

###### **7.4.1.1. Clinical Response at End of IV Treatment (EOIVT) and End of Treatment (EOT)**

Clinical response is defined as follows:

- **Cure**: Resolution of signs and symptoms attributed to *Candida* infection; no additional systemic antifungal;
- **Improvement**: Significant, but incomplete resolution of signs and symptoms of the *Candida* infection; no additional systemic antifungal;
- **Failure**: No significant improvement in signs and symptoms, or death due to the *Candida* infection. Subjects must have received at least 3 doses of study medication to be classified as a failure;
- **Indeterminate**: Evaluation cannot be made due to withdrawal from the study prior to assessment of cure or failure. Subjects who receive fewer than 3 doses of study medication will be assigned a clinical efficacy response of indeterminate.

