###### **7.4.1.2. Microbiologic Response at End of IV Treatment (EOIVT) and End of Treatment (EOT)**

Microbiologic response is defined as follows:

- **Eradication or presumed eradication**: Baseline pathogen not isolated from original site culture(s), or culture data are not available for a subject with successful outcome.
- **Persistence (documented or presumed)**: Any baseline *Candida* spp. is present in repeat cultures, or culture data are not available for subject with a clinical outcome of failure.
- **Indeterminate**: Culture data are not available for a subject with a clinical outcome of indeterminate.

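### Protocol 6.10 calls candidemia beyond 7 days a treatment failure, but no global-response rule carries this, so such a child can be analysed as a success at EOIVT or EOT

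*SAP*

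**What the plan says.** Protocol 6.10 sets a rule based on duration. It covers "Subjects who were either candidemic at baseline or become candidemic during the course of the study", and says these subjects "will be considered treatment failures and discontinued from study treatment if candidemia persists for more than 7 days". It is not limited to the species found at baseline.

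The endpoint is defined elsewhere. Protocol 7.3 states: "A subject will be categorized as a success if there is both a clinical success (cure or improvement) and microbiological success"; and "A subject will be categorized as a failure if there is either a clinical or microbiological failure". In Protocol 7.4.1.1, clinical failure is "No significant improvement in signs and symptoms, or death due to the" *Candida* infection, while cure and improvement carry the condition "no additional systemic antifungal". Eradication, in Protocol 7.4.1.2, is "Baseline pathogen not isolated from original site culture(s), or culture data are not available for a subject with successful outcome". Persistence there means baseline *Candida* in repeat cultures, or no culture in a clinical failure. None of these clauses mentions how long blood cultures stayed positive.

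The SAP follows the same structure. Under 6.1.1.1, "Global response at EOIVT is based on assessment of clinical and microbiological response provided by the investigator at this time point"; 6.1.2 applies the same definitions at EOT. The one programmed override of the investigator's category, in 6.1.4, concerns other antifungals and acts on visits after they were taken. A note in 6.1.1.2 treats antifungal use after EOT as clinical failure unless it is clearly prophylactic.

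**The concern.** The protocol makes two statements about the same child, and the analysis implements only one. Section 6.10 declares failure from the course of blood cultures over time. The programmed endpoint looks at two investigator categories at one visit. Where the two disagree, the visit categories prevail without comment, in an open-label trial where the rater knows the treatment.

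At stake is the success rate at EOIVT and EOT. The discrepancy runs one way: a 6.10 failure can be counted as a success, and nothing in the missing rule could turn a failure into a success.

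**Working it through.** The plan has no figure to reproduce: Protocol 9.4 says no sample size calculation was done, and no stated number depends on this rule. The check applies the SAP derivation to each possible case.

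**Step 1: the SAP derivation.** Take a child rated cure or improvement at EOIVT or EOT, and read the microbiological category from the culture at that visit (SAP 6.1.1.1 and 6.1.1.2).

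| Culture at the visit | Microbiological category | Global response |
|---|---|---|
| Baseline species grown | Persistence | Failure |
| Negative | Eradication | Success |
| Only a non-baseline species grown | Eradication | Success |
| Not taken | Presumed eradication | Success |

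If the clinical rating is failure, every row is a failure.

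**Step 2: how a 6.10 failure reaches a success row.**
- Blood is positive beyond 7 days, but the culture at the visit is negative.
- No culture is taken when treatment stops early. Protocol 7.8.5 asks for one at premature discontinuation only when clinically indicated, whereas Protocol 6.7 calls for all EOT procedures, which include blood culture. These passages need reconciling.
- Candidemia on treatment is due to a new species. Section 6.10 covers it, but persistence is limited to baseline *Candida*, and SAP 6.1.1.1 counts new infection only at follow-up.

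**Step 3: the override.** Under SAP 6.1.4, an antifungal started after the EOIVT or EOT visit leaves that visit unchanged. In follow-up it imputes failure only if the clinical team attributes it to lack of efficacy. With success recorded at EOIVT and EOT, there is no failure to carry forward.

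**Step 4: size.** Planned numbers are about 60 evaluable subjects (SAP 2.1.2) and 20 ± 2 per age stratum (SAP 3.1). One reclassified child moves the rate by 1/60 = 1.7 points overall, or 1/20 = 5 points in a stratum.

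As an illustration only, assume the adult pivotal trial's 75.6% success at EOIVT (Protocol 1.3.2): 0.756 × 60 ≈ 45 and 0.756 × 20 ≈ 15. The intervals are exact Clopper-Pearson, as in SAP 8.1.1.

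| Children moved to failure | Of 60 (95% CI) | Of 20 (95% CI) |
|---|---|---|
| 0 | 75.0% (62.1 to 85.3) | 75.0% (50.9 to 91.3) |
| 1 | 73.3% (60.3 to 83.9) | 70.0% (45.7 to 88.1) |
| 3 | 70.0% (56.8 to 81.2) | 60.0% (36.1 to 80.9) |

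**Step 5: can 6.10 be derived as written?** It does not say when the 7 days start, and cultures may be 3 days apart (Protocol 7.8.5). Take positives on Day 1 and Day 7 and a negative on Day 10. Counted from Day 1, candidemia ended between 7 − 1 = 6 and 10 − 1 = 9 days later, so the criterion is undecided. Counted from a qualifying culture drawn 96 hours before a Day 1 screening visit, the Day 7 positive is already 4 + 6 = 10 days out.

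**The case against.** The best reply is that the SAP already excludes these children from success. In 6.1.1.2, cure and improvement require that no further antifungal is needed to finish the course. A child stopped for prolonged candidemia has not had the 14 days of treatment after the last negative culture, and so still needs therapy. The note in the same section then makes non-prophylactic use after EOT a clinical failure. Applied as written, this would catch a child with late positive baseline-species cultures who turns negative and improves by the stop. A reader might infer that such a child is certain to be scored a success; the documents do not support that.

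The reply does not close the gap. The note names no visit, and it sits uneasily with SAP 6.1.4, which acts only on visits after the drug was taken. The clinical category remains the investigator's, and a child who improves but needs more therapy fits neither improvement nor the wording of clinical failure.

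A second reply is that positives in any repeat on-treatment culture are persistence. That would catch every baseline-species case. It would also fail a child with a single positive Day 3 culture, which fits neither the 7-day allowance in 6.10 nor the SAP's reliance on the assessment at the visit. It leaves the new-species route open.

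A third reply is that the investigator who stops treatment under 6.10 also assigns the category and would normally record failure. This stands as a reason to expect few cases.

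**Conclusion.** The point holds as a conflict between two stated rules. A child whom 6.10 declares a failure can be analysed as a success at EOIVT and EOT, through a negative or missing last culture or a non-baseline species. It need not be usual.

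Three stronger readings are not supported:
- That 6.10 failures would routinely be scored as successes. Persistence and the antifungal conditions will catch some or most.
- That 6.10 is the trial's only rule-based efficacy failure. SAP 6.1.4 and the carry-forward of failures are also rules; 6.10 is the only one based on culture duration.
- That a total bias can be stated. The documents give no frequency of candidemia beyond 7 days, and some evaluable subjects have sterile-site infection without candidemia, so multiplying an assumed frequency by 60 would be guesswork.

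What can be said is 1.7 points per child of 60, or 5 per child in a stratum of 20, and the error can only raise the success rate. Global response is secondary and descriptive, no hypothesis is tested, and the primary safety analysis is unaffected.

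**What to change.** Add to SAP 6.1.1.1, and to Protocol 7.3, a programmed rule: any subject meeting Protocol 6.10, derived from recorded blood-culture dates and counting non-baseline *Candida* species, is a global failure at EOIVT and all later visits, whatever category the investigator assigned.

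The SAP should also:
- state when the 7-day count starts and how gaps between cultures are handled, consistently with 6.10;
- say from which visit failure applies if the criterion is first met during oral therapy;
- reconcile the note in 6.1.1.2 with the timing in 6.1.4, so that it is clear which visits become failures.

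Protocol 6.7 and 7.8.5 should be reconciled on the culture at early stopping. If the sponsor does not intend 6.10 to define an endpoint failure, the SAP should say so and report these subjects separately.

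The cost is a short SAP amendment, matching protocol text and one derivation. SAP 8.2.4.8 already uses the date of the last positive blood culture, so no new data appear to be needed. The success rate may be slightly lower. Only the analysis classification changes; the clinical discontinuation rule is not altered.

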#### 7.4.1.4. Microbiologic Response at the 2-Week and 6-Week Follow-Up Visits

Microbiologic response is defined as follows:

- **Eradication or presumed eradication**: Baseline pathogen not isolated from original site culture(s), or culture data are not available for a subject with successful outcome;
- **Persistence (documented or presumed)**: Any baseline *Candida* spp. is present in repeat cultures, or culture data are not available for subject with a clinical outcome of failure;
- **Indeterminate**: Culture data are not available for a subject with a clinical outcome of indeterminate;
- **Relapse (recurrence)**: Any baseline *Candida* spp isolated following eradication (documented or presumed); or culture data are not available for a subject with a clinical response of failure after a previous response of success;
- **New Infection**: Subject presenting with clinical failure with the emergence of new *Candida* spp at the original site of infection or at a distant site of infection.

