#### **Microbiological Response**

**Eradication or presumed eradication:** Baseline pathogen not isolated from original site culture(s), or culture data are not available for a subject with successful clinical outcome.

**Persistence (documented or presumed):** Any baseline *Candida* sp. is present in repeat cultures, or culture data are not available for subject with a clinical outcome of failure.

**Indeterminate:** Culture data are not available for a subject with a clinical outcome of indeterminate.

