### 6.1.2. Global Response at the End of all Treatment (EOT)

Global response at EOT will be programmatically determined utilizing the same global response, clinical response and microbiologic response definitions for EOIVT, described in [Section 6.1.1.1](#) and [Section 6.1.1.2](#).

A global response determination of failure at EOT will be carried forward programmatically to all subsequent visits.

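### At EOIVT and EOT a Candida species not present at baseline has no microbiological failure category, so a first positive culture at that visit can be scored as a global success

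*SAP*

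**What the plan says.** **Global response.** SAP 6.1.1.1 derives it from the investigator's two ratings. Success needs a "clinical response of cure or improvement and microbiological eradication or presumed eradication". Failure needs clinical failure or an "unsuccessful microbiological response (persistence or new infection at FU or relapse at FU"). The Indeterminate rule in the same section also lists new infection and relapse, but without the limit to follow-up.

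**Microbiological response at EOIVT.** SAP 6.1.1.2 defines eradication as "Baseline pathogen not isolated from original site culture(s), or culture data are not available for a subject with successful clinical outcome". Persistence needs a baseline species or missing cultures; Protocol 7.4.1.2 words it as "Any baseline *Candida* spp. is present in repeat cultures, or culture data are not available for subject with a clinical outcome of failure". Indeterminate needs missing cultures together with an indeterminate clinical outcome. Protocol 7.4.2.2 repeats these categories for endocarditis and osteomyelitis.

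**EOT.** SAP 6.1.2 derives the result "utilizing the same global response, clinical response and microbiologic response definitions for EOIVT".

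**Follow-up.** Protocol 7.4.1.4 and 7.4.2.4 and SAP 6.1.3 add relapse and new infection. New infection is a "Subject presenting with clinical failure with the emergence of new *Candida* spp at the original site of infection or at a distant site of infection". Relapse is met by isolating a baseline species after eradication, with no clinical condition.

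**Reporting.** The microbiological summary in SAP 8.2.2 has no row for new infection or relapse. New-infection rates are planned for Weeks 2 and 6 only.

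**The concern.** A new Candida species growing from blood or another sterile site during treatment is an unsuccessful microbiological result by the SAP's own principle, since the SAP classes new infection that way at follow-up. At EOIVT and EOT the wording gives the opposite answer. Eradication asks only whether the baseline organism has gone from the original site, and no category asks what else grew. Protocol 6.10 foresees the event, since it refers to "Subjects who were either candidemic at baseline or become candidemic during the course of the study".

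At stake are the global response rates at EOIVT and EOT, where any error can only favour the drug, and in a single-arm study no comparator offsets it. A new species that emerges on treatment also appears in no new-infection table. Efficacy is secondary and descriptive here, so no test or decision rule is affected.

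**Working it through.** The plan states no figure for this, so there is nothing to reproduce. The check applies the definitions literally.

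**Step 1. Classify a culture growing only a new species** (no baseline species, no other antifungal taken).

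| Visit | Clinical rating | Microbiological category | Global response |
|---|---|---|---|
| EOIVT, EOT | cure or improvement | eradication | success |
| EOIVT, EOT | indeterminate | eradication | indeterminate |
| EOIVT, EOT | failure | eradication | failure, by the clinical arm only |
| Follow-up | cure or improvement | eradication | success |
| Follow-up | indeterminate | eradication | indeterminate |
| Follow-up | failure | new infection | failure |

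If the baseline species also grows, persistence applies and the child is a failure. At follow-up, new infection never changes global response by itself, because clinical failure is already part of its definition.

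**Step 2. Which children reach the success row at EOIVT or EOT?**

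- Clinical definitions (SAP 6.1.1.2): cure and improvement both require that no further antifungal treatment is needed to finish the course. A child known to need more therapy for a new species does not qualify.
- SAP 6.1.4: other antifungal use up to EOT (two or more days for any reason, or one day for lack of efficacy) sets failure, but only for visits after the drug was taken. Its lead-in refers to activity against a baseline species.
- Protocol 6.10: candidemia persisting beyond 7 days is a treatment failure, whatever the species. It does not reach shorter episodes or sites other than blood, and the SAP does not program it.
- Timing: EOIVT procedures fall on the last IV day or within 24 hours of it (Protocol 6.3), while cultures not yet positive are incubated for at least five days (Protocol 7.8.5). The rating can precede the result, and I found no instruction to revisit it.

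The residual case is therefore mainly a first positive culture at the EOIVT or EOT visit in a child already rated cure or improvement.

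**Step 3. Size per case.** Change in success rate = 1/n.

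- About 60 evaluable subjects (Protocol 9.4): 1/60 = 1.7 points.
- A stratum of 20 ± 2 (Protocol 9.6): 1/20 = 5 points; range 1/22 = 4.5 to 1/18 = 5.6.

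**Step 4. Illustration** with the Clopper-Pearson 95% interval of SAP 8.1.1. Assumption, not from the documents: 75% are scored as success, and k of them grew a new species.

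| k moved to failure | 45 of 60 before the move | 15 of 20 before the move |
|---|---|---|
| 0 | 75.0% (62.1 to 85.3) | 75.0% (50.9 to 91.3) |
| 1 | 73.3% (60.3 to 83.9) | 70.0% (45.7 to 88.1) |
| 2 | 71.7% (58.6 to 82.5) | 65.0% (40.8 to 84.6) |
| 3 | 70.0% (56.8 to 81.2) | 60.0% (36.1 to 80.9) |

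**The case against.** The strongest reply is that a reader might infer from the table that breakthrough infection in general is analysed as success. The documents do not support that. Cure and improvement turn on whether further treatment is required, not only on whether it was taken, and antifungal use after EOT that is not clearly prophylactic is clinical failure (notes in SAP 6.1.1.2 and 6.1.3). The treatment rules also make the case uncommon. For confirmed infection, the oral switch needs two blood cultures negative for any Candida, and minimum duration runs from the second of two consecutive negatives after the last positive (Protocol 3 and 5.1). All this stands, and it confines the point to a late first positive culture. One qualification: in Protocol 7.4.2.1, for endocarditis and osteomyelitis, improvement carries no condition on further antifungals.

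A reader might also infer that the follow-up definition hides many proven cases. That is weakly supported. Follow-up cultures are taken only when clinically indicated (Protocol 6.5 and 6.6), and a child then treated for infection becomes a clinical failure and so meets the definition.

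Finally, microbiological response is the investigator's rating, and the mismatch within SAP 6.1.1.1 suggests loose drafting rather than a deliberate rule. That is fair, but an investigator following the definitions has no unsuccessful category to choose, so the result may differ between sites.

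**Conclusion.** The gap is real and narrow. At EOIVT and EOT a new species alone has no microbiological failure category, and with a rating of cure or improvement the stated rule returns global success. Each such child is worth 1.7 points of 60, or 5 points in a stratum of 20, in the favourable direction.

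The documents give no emergence rate, so no total bias can be stated. In the illustration, moving three of 60 takes 75.0% to 70.0%, which is inside the original interval. The conclusion rests on a literal reading of the definitions and on the ratings not being revised once the culture is final. The change is worth making because the error runs one way and is cheap to remove. It does not touch the primary safety objective.

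**What to change.** 1. Add a category to the EOIVT and EOT microbiological definitions (Protocol 7.4.1.2 and 7.4.2.2; SAP 6.1.1.2, and through it 6.1.2): *New infection: a Candida species not present at baseline isolated from blood or another normally sterile site.*
2. In the SAP 6.1.1.1 failure rule, remove the follow-up limit after new infection, so that it agrees with the Indeterminate rule.
3. Add new-infection and relapse rows to the microbiological summary in SAP 8.2.2.
4. Reconcile Protocol 6.10 with the SAP derivation, stating whether and how that failure rule enters global response.
5. At follow-up, keep the present new-infection definition. Add a sensitivity analysis of global response and of the new-infection rate that counts any sterile-site isolate of a new species whatever the clinical rating, using the recorded and reference-laboratory species.

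The cost is wording in both documents, a small change to the derivation, and one sensitivity analysis that links isolates to visits. Protocol 7.8.5 already sends all sterile-site Candida isolates to the reference laboratory, so no new sampling is needed. The sensitivity analysis departs from the investigator-rated approach and should be labelled as such. The downside is that the success rate may fall slightly and the new-infection rate may rise slightly.
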